7.2.1. Treatments Administered

Table JGDM.1 shows the treatment regimens to be administered in this study.

Table JGDM.1. Treatment Regimens

Treatment	Cycle Length (Days)	Study Drug	Dose	Timing	Route
Monotherapy Cycle 1	21	Olaratumab ^a	20 mg/kg	approximately 1 hour infusion D1, D8	IV
		1-hour (\pm 5 minutes) Observation Period ^b			
Combination Therapy Cycle 2	21	Olaratumab ^a	20 mg/kg	approximately 1 hour infusion D1, D8	IV
		1-hour (\pm 5 minutes) Observation Period ^b followed by			
		Doxorubicin ^c	75 mg/m ²	IV injection on D1	IV
Combination Therapy Cycle 3 – Cycle 7	21	Olaratumab ^a	15 mg/kg	approximately 1 hour infusion D1, D8	IV
		Doxorubicin ^c	75 mg/m ²	IV injection on D1	IV

Abbreviations: D = day; eCRF = electronic case report form; IRR = infusion-related reaction; IV = intravenous; PO = orally.

- ^a Premedicate all patients with the following (or equivalent) medications: a histamine H1 antagonist (for example, diphenhydramine) and dexamethasone intravenously 30–60 minutes prior to the olaratumab doses on Days 1 and 8 of Cycle 1. For subsequent cycles, premedicate all patients with a histamine H1 antagonist (for example, diphenhydramine) intravenously 30–60 minutes prior to each dose of olaratumab. Additional premedication may be provided at the investigator's discretion. Premedication **must be** provided in the setting of a prior Grade 1-2 IRR, as detailed in Section 7.2.2 and Section 7.2.3.1.1.1. All premedication administered must be adequately documented in the eCRF.
- ^b A 1-hour (+5 minutes) Observation Period is required after the administration of the initial 2 cycles of olaratumab. During the Observation Period, collect vital signs 3 times: 1) within 15 minutes (+5 minutes) prior to olaratumab infusion, 2) within 1 hour (+5 minutes) after completion of the olaratumab infusion, and 3) within 1 hour (+5 minutes) after completion of the doxorubicin infusion. If no evidence of an IRR manifests during the initial 2 cycles of olaratumab, then no observation period is required for subsequent treatment cycles. In the event an IRR occurs thereafter, then the 1-hour Observation Period should be reinstated; see Section 7.1.2. Thereafter (Cycles 3+), obtain vital signs 2 times: 1) within 15 minutes (+5 minutes) prior to olaratumab infusion and 2) within 1 hour (+5 minutes) after completion of the doxorubicin infusion.

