5.1. Study Design and Sample Size Consideration

Study JGDM is an open-label, single-arm, multicenter, multicountry Phase 1b study to enumerate whole blood CTCs and to characterize PDGFR α and PDGFR β and canonical ligands (*PDGF-A, B, C* and *D*) expression changes pre- and post-olatumab monotherapy in tumor tissue in patients with potentially resectable STS.

Patients are to be treated with 20 mg/kg of olatumab on Day 1 and Day 8 of Cycle 1, followed by up to 6 cycles (Cycle 2 – Cycle 7) of combination therapy with olatumab plus doxorubicin. For Cycle 2, olatumab is to be dosed at 20 mg/kg on Day 1 and Day 8 and doxorubicin is to be dosed at 75 mg/m² on Day 1. For Cycle 3 – Cycle 7, olatumab is to be dosed at 15 mg/kg on Day 1 and Day 8 and doxorubicin is to be dosed at 75 mg/m² on Day 1. Each cycle of treatment is defined as an interval of 21 days. Approximately 35 patients are to be enrolled.

Starting with the first cycle of combination therapy (Cycle 2), the use of dexrazoxane (in a 10:1 ratio vs. doxorubicin dose) to mitigate cardiotoxicity during treatment with doxorubicin is allowed at the investigator's discretion and is recommended for all patients receiving 5 or more cycles of doxorubicin.

Tissue biopsies are required pre- and posttreatment with olatumab monotherapy. The pretreatment tissue biopsy is to be performed within the screening period. The posttreatment tissue biopsy is to be performed after completion of the lead-in cycle of olatumab monotherapy and prior to the initiation of combination therapy in Cycle 2. An optional third tissue biopsy (or tissue from a posttherapy surgical resection specimen) may be performed at the end of the patient's study treatment. If clinically feasible, the tissue biopsies should be taken from the same primary tumor lesion. If the patient has an additional surgical resection, tissue from this procedure is requested. Refer to Protocol Section 8.2.3.2 for details on tissue biopsies.

Whole blood samples for CTC analyses are to be collected predose at Cycle 1 Day 1 (C1D1), at Cycle 1 Day 8 (C1D8), at Cycle 2 Day 1 (C2D1), at Cycle 2 Day 8 (C2D8), at Cycle 3 Day 1 (C3D1), and at the end of the patient's study treatment or at the time of surgical resection. Refer to Protocol Section 8.2.3.1 for details on blood samples.

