5.11.1. Study Drug Exposure

Study drug exposure will be summarized based on Safety Population. The summary will include duration of treatment, number of infusions, the number of cycles received per patient, cumulative dose, cumulative dose level, weekly dose intensity, relative dose intensity, by assigned treatment. Details of study drug administration will be included in patient listings.

Dose modifications, delays and discontinuations will also be summarized.

The exposure formulas are defined below.

Olaratumab:

- Duration of treatment (weeks) = $([\text{Date of last dose} - \text{date of first dose}] + 21) \div 7$
- Cumulative dose (mg) = Sum of all doses
- Calculated dose level administered (mg/kg) = $\frac{\text{Actual total dose of olaratumab (mg)}}{\text{Closest body weight prior to that administration (kg)}}$
Cumulative dose level (mg/kg) = Sum of all calculated infusion doses
- Dose intensity (mg/kg/week) = $(\text{Cumulative dose level}) \div (\text{Duration of treatment})$
- Planned dose intensity (mg/kg/week)
 - Cycle 1 = 20 mg/kg/three weeks
 - Cycle 2 = 20 mg/kg/three weeks
 - Cycle 3-7 = 15mg/kg/three weeks

- Relative dose intensity (%) (Based on planned dose)= (Dose intensity) ÷ (Planned dose intensity) x 100

Doxorubicin:

- Duration of treatment (weeks) = ([Date of last dose – date of first dose] + 21) ÷ 7
- Cumulative dose (mg) = Sum of all doses
- Cumulative dose level (mg/m²) = Sum of (dose administered at each infusion [mg] ÷ Last available body surface area [BSA] [m²] prior to that infusion)
- BSA (m²) = 0.007184 * weight (kg) ^0.425 * height (cm) ^0.725
- Dose intensity (mg/m²/weeks) =(Cumulative dose level) ÷ (Duration of treatment)
- Planned dose intensity (mg/m²/week) = 75 mg/m²/ 3 weeks= 25 (Cycle 2-7)
- Relative dose intensity (%)=(Dose intensity) ÷ (Dose intensity) x 100

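### SAP 5.11.1 plans olaratumab dose intensity on one of the two infusions per cycle, so a fully dosed patient cannot read 100%

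*SAP*

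**What the plan says.** **Olaratumab, SAP 5.11.1.** The numerator is "Cumulative dose level (mg/kg) = Sum of all calculated infusion doses". Dose intensity divides this by a duration in weeks, which is the days from first to last dose plus 21, divided by 7. RDI is dose intensity over planned dose intensity. The plan is headed "Planned dose intensity (mg/kg/week" (the unit bracket closes there), and its entries include "Cycle 1 = 20 mg/kg/three weeks" and "Cycle 3-7 = 15mg/kg/three weeks"; Cycle 2 matches Cycle 1.

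**Regimen.** SAP 5.1 gives olaratumab "on Day 1 and Day 8 of Cycle 1, followed by up to 6 cycles" of combination therapy, with Day 1 and Day 8 infusions in those cycles too. Protocol Table JGDM.1 (section 7.2.1) lists "approximately 1 hour infusion D1, D8" for every cycle. Protocol 6.2 agrees. Cycles last 21 days.

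**Doxorubicin, SAP 5.11.1.** The plan is converted to a weekly figure, ending "3 weeks= 25 (Cycle 2-7" (again a bracket). The ratio is printed as "Relative dose intensity (%)=(Dose intensity) ÷ (Dose intensity) x 100".

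**The concern.** The numerator and the plan describe different things. The numerator counts two infusions per cycle and the plan counts one, so RDI is twice what it should be for any given duration. The plan entries are also per three weeks under a per-week label, so a programmer must choose between two denominators that differ threefold. The SAP does not say how the cycle-specific plans combine into one value per patient.

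What is at stake is the meaning of one named output. RDI should show how much of the scheduled drug was delivered. As defined, full delivery looks like overdosing (or, in the labelled unit, underdosing), and a patient given half the scheduled olaratumab looks fully compliant. Missed Day 8 doses are foreseeable: protocol 7.2.3.1 directs that the Day 8 dose be skipped if neutrophils do not recover within 7 days.

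**Working it through.** **Inputs.** 20 mg/kg per infusion in Cycles 1-2 and 15 in Cycles 3-7, Day 1 and Day 8, 21-day cycles (SAP 5.1, protocol Table JGDM.1). Numerator, duration and plan are from SAP 5.11.1. I assume on-time dosing and constant weight. For seven cycles I average the plans over cycles, because the SAP gives no rule. One- and two-cycle results need no averaging, since those plans are equal.

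**Reproducing the plan.**
- Olaratumab, Cycle 1: one infusion gives 20/3 = 6.67 mg/kg/week, the SAP value after unit conversion. Two infusions give 40/3 = 13.33. The SAP value is reproduced only with a single infusion.
- Doxorubicin: 75/3 = 25 mg/m²/week, reproduced exactly.

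**RDI as written, full compliance.** After n cycles the last dose falls 21(n-1) + 7 days after the first, so SAP duration is (21(n-1) + 7 + 21)/7 = 3n + 1 weeks. The seven-cycle dose is 4 × 20 + 10 × 15 = 230 mg/kg. The averaged SAP plan is (2 × 20 + 5 × 15)/21 = 115/21 = 5.476 mg/kg/week.

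| Cycles | Dose (mg/kg) | Duration (wk) | Intensity (mg/kg/wk) | SAP plan (mg/kg/wk) | RDI |
|---|---|---|---|---|---|
| 1 | 40 | 4 | 10.0 | 6.667 | 150.0% |
| 2 | 80 | 7 | 11.429 | 6.667 | 171.4% |
| 7 | 230 | 22 | 10.455 | 5.476 | 190.9% |

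**Labelled unit.** Taking 20, 20 and 15 as mg/kg/week: 10.0/20 = 50.0% (1 cycle), 11.429/20 = 57.1% (2), and 10.455/(115/7 = 16.429) = 63.6% (7).

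**Every Day 8 dose missed, seven cycles.** Dose is 115 mg/kg and duration (126 + 21)/7 = 21 weeks. 115/21 = 5.476, which reads 100% against the SAP plan and 50% against the two-infusion plan.

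**Correcting only the plan.** The two-infusion plan is 13.33 in Cycles 1-2 and 30/3 = 10 in Cycles 3-7, averaging 230/21 = 10.952 over seven. Full compliance then reads 10.0/13.33 = 75.0% (1 cycle), 11.429/13.33 = 85.7% (2) and 10.455/10.952 = 95.5% (7). The shortfall is the extra week: a Day 8 dose has 14 days of its cycle left, not 21.

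**Correcting plan and duration.** With 14 days added after a Day 8 last dose, durations are 3, 6 and 21 weeks. Then 40/3 against 13.33, 80/6 against 13.33 and 230/21 against 10.952 all give 100%. With Cycle 2 of three withheld, the dose is 70 mg/kg over 9 weeks = 7.778, against 110/9 = 12.222, or 63.6%, which is the share delivered (70/110).

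**Doxorubicin.** Six cycles at 60 mg/m²: 360/18 weeks = 20, and 20/25 = 80%. The printed ratio, taken literally, gives 20/20 = 100%.

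**The case against.** The best counter-argument is about importance. SAP 5.2 calls the analyses descriptive and the trial has one arm, so no between-arm exposure comparison can be distorted. Infusions, cycles, cumulative dose, weekly intensity, omissions, reductions and delays are reported separately under SAP 5.8 and 5.11.1, with patient listings. Values of 150% to 191% would be conspicuous in any output check. All of this stands and limits the consequence. It does not make the formula right, and a reading of 100% in a patient who missed every Day 8 dose would not look odd.

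It can also be said that, without an averaging rule and with an ambiguous unit, the SAP implies no single wrong value. That is fair for seven cycles. It does not rescue the plan, because neither reading of the unit gives 100% at full compliance, even at one or two cycles.

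A third objection is that no fix yields 100% in practice. Protocol 7.3.1 tolerates 3-day cycle delays. If Cycles 2 to 7 each start 3 days late, duration is 147 + 18 = 165 days and corrected RDI is 147/165 = 89.1%. This fails as an objection: RDI is meant to fall with delay.

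A reader might infer three stronger things that the documents do not support:
- **That doxorubicin RDI will be 100% for everyone.** The planned value of 25 is defined on the line above and the olaratumab ratio is printed correctly, so this is almost certainly a dropped word.
- **That the regimen itself is in doubt.** Protocol 6.2, Table JGDM.1 and SAP 5.1 agree; only the exposure formula departs from them.
- **That patients will be ranked wrongly.** Examples can be built, because the extra week weighs more in short courses, but they need an assumed averaging rule and a particular dosing history. Nothing in the documents shows this to be likely.

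**Conclusion.** The olaratumab planned dose intensity is wrong as written. It counts one of two scheduled infusions and carries a conflicting unit, and no other section corrects it. At full, on-time compliance RDI reads 150.0% to 190.9% with the unit converted, or 50.0% to 63.6% in the labelled unit. The one- and two-cycle figures follow directly from the SAP formulas; the seven-cycle figures also assume averaging over cycles. All assume exact 21-day cycles and constant weight.

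The effect stops at the descriptive exposure summary. The biomarker endpoints, their evaluable populations, the sample size and the efficacy analyses do not use RDI. The correction should be made because RDI is a named output and the repair is cheap, not because any trial conclusion depends on it.

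**What to change.** Amend the formulas in SAP 5.11.1:

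1. **Olaratumab plan.** Use both scheduled infusions divided by 3 weeks: 13.33 mg/kg/week in Cycles 1-2 and 10 in Cycles 3-7. Average over all cycles from the first through the last in which olaratumab was given, including any cycle in between in which it was withheld. If RDI is split into Cycle 1 and Cycle 2 onward, as SAP 5.11 allows for selected analyses, apply the same rule within each part.
2. **Olaratumab duration.** Add 14 days instead of 21 when the last dose is a Day 8 dose. This keeps the last-dose anchor, so it stays defined when the two drugs are delayed separately (protocol 7.2.3.1).
3. **Doxorubicin (minor erratum).** Divide by planned dose intensity, 25 mg/m²/week.

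**Cost.** No new data, no protocol change, and no change to any dose or clinical rule. Step 2 also alters two other named outputs, which the SAP should state. For one full cycle, olaratumab duration becomes 3 weeks instead of 4 and weekly intensity 13.33 instead of 10.0 mg/kg/week. For seven cycles they become 21 instead of 22 weeks and 10.952 instead of 10.455.

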5.11.2. Adverse Events

Adverse events will be coded using the MedDRA dictionary. Severity grades will be assigned by investigators using the NCI-CTCAE Version 4.0.

The AE analysis variables have been specified in Section 5.3.4.

Study drug-related AEs are AEs that were considered to be at least possibly related to study drug by an investigator. See section 5.4 pertaining to missing data.

The most current version of MedDRA at time of analysis will be used when reporting AEs by MedDRA terms. Unless otherwise specified, when summarized by PT, AEs will be presented in descending frequency of PT across treatment arms; when summarized by system organ class (SOC) and PT, AEs will be presented in descending frequency of PT within SOC across treatment arms. If more than one AE is recorded for a patient within any SOC or PT term, the patient will only be counted once on the most severe grade and the closest relationship to treatment.

An overall summary of AEs will be provided to summarize the following categories using frequency counts and percentages by assigned treatment:

- patients with at least one treatment-emergent adverse event (TEAE), serious adverse event (SAE), or CTCAE Grade 3 or 4 TEAE
- patients with AEs that led to death (all, up to 30 days after last dose of study drug), or discontinuation of study drug regimen

The summary will be provided for regardless of study drug causality, and repeated for events deemed by the investigator to be related to study treatment.

Treatment-emergent adverse events (TEAEs) will be summarized/listed as follows:

- treatment-emergent AE by system organ class (SOC) and PT

- study drug related TEAE
- summary of TEAEs by worst CTCAE grade
- consolidated TEAEs by consolidated category and PT
- study drug related consolidated TEAE
- summary of TEAEs by PT and descending frequency
- listing of TEAE leading to death (on treatment and within 30 days of last dose of study drug)
- listing of TEAE leading to discontinuation of olaratumab, chemotherapy, or any study drug
- listing of TEAEs leading to dose modification of any study drug, olaratumab, or chemotherapy

A patient listing of all AEs will be provided.

The following treatment-emergent SAE summaries will be provided:

- summary of treatment-emergent SAE by SOC and PT
- summary of study drug-related treatment-emergent SAE by SOC and PT
- summary of consolidated treatment-emergent SAEs
- summary of study drug-related consolidated treatment-emergent SAEs

A listing of SAEs will be produced.

The following death reports will be provided:

- summary of deaths (all deaths and deaths within 30 days of last dose of study drug)

The following AE of special interest (AESIs) summary will be provided:

- summary of treatment-emergent AESIs by AESI group and PT (regardless of causality and study drug-related)
- listing of treatment-emergent AESIs

5.11.3. Clinical Laboratory Evaluation

The severity of laboratory results will be classified according to CTCAE Version 4.0. The shifts in CTCAE toxicity grading from baseline to worst postbaseline (first dose up to 30 days after the last dose of study treatment) grade will be produced.

A patient listing of all laboratory data will be provided with a flag for values outside of the laboratory normal range.

5.11.4. Vital Signs, Physical Findings, and Other Observations Related to Safety

Actual value and change from baseline for vital sign measurements will be summarized at each assessment time point using summary statistics. Electrocardiogram, Echocardiogram(ECHO)/MUGA measurements will also be summarized at each assessment time point using summary statistics. Listings of vital signs, ECG, ECHO/MUGA and data will be provided.

5.12. Pharmacokinetic Analyses

Serum concentrations of olaratumab prior to infusion (minimum concentration) and immediately after the end of the olaratumab infusion (approximately maximum concentration) will be summarized by descriptive statistics or visually presented. Additionally, PK parameter estimates will be computed by standard noncompartmental methods of analysis for olaratumab PK samples collected during cycle 2. The maximum concentration (C_{max}), time of C_{max} (t_{max}), area under the concentration-time curve (AUC), half life (t_{1/2}), volume of distribution (V_d), clearance (CL), and other relevant parameters that can be calculated from the data will be reported from these noncompartmental analyses. Additional analyses utilizing the population pharmacokinetic approach may also be conducted if deemed appropriate.

5.13. Immunogenicity

The immunogenicity analyses will be conducted on all immunogenicity evaluable patients (evaluable population) within the defined safety population. The frequency and percentage (incidence) of evaluable patients with positive, negative, or missing anti-drug antibody (ADA), to olaratumab at baseline, and with positive, negative, or inconclusive ADA at post-baseline will be summarized by dose cohort and combination treatment arm. Patients who are TE (treatment-emergent)-ADA positive (persistent positive or transient positive), TE-ADA persistent positive, and TE-ADA transient positive will also be summarized. Positive neutralizing ADA, negative neutralizing ADA and inconclusive neutralizing ADA will also be reported for patients with TE positive ADA. Quantitative analysis will be conducted on total IgE and alpha-Gal. Analyses will include change from baseline, mean, median, range and standard deviation.

The following analyses will also be performed based on evaluable or safety population:

- Listing of Treatment-Emergent Adverse Events for evaluable patients with at least one sample of ADA positive antibody to olaratumab (evaluable population)
- Listing of antibody to olaratumab and drug concentration data for evaluable patients who have at least one ADA positive sample (evaluable population)
- Listing of anti-olaratumab antibody for patients with IRR (safety population)
- Listing of antibody to olaratumab and drug concentration data (safety population)

Listing for alpha-Gal and IgE (safety population)

The potential impact of immunogenicity on olaratumab exposure will be evaluated in the population PK modeling exercises where immunogenicity will be evaluated as a covariate. In addition, graphical assessments will be conducted, as appropriate, to compare drug exposure between TE-ADA-negative and TE-ADA-positive patients at correspondent visits, or before and after TE-ADA development for patients who developed TE-ADA.

Additional efficacy or safety analyses may be performed in the subgroup of patients and immunogenicity endpoints.

5.14. Interim Analysis

With limited prior experience with the performance of the biomarker assays (i.e, QC issues, dynamic range, data variability), an interim analysis will be done to evaluate the biomarker data once approximately half of the evaluable patients complete the second tumor tissue biopsy and C2D1 whole blood draw. The purpose of this interim analysis is to review the biomarker data in order to identify technical issues that may potentially impact the study's ability to meet its key objectives. If this interim look at the biomarker data warrants any changes in the study conduct, it will be implemented in an appropriate manner (that is, protocol amendment). At this interim analysis, a review of the safety data will also be conducted.

This would be in addition to the safety data review that will be conducted after 5 patients have completed 2 cycles of treatment.

5.15. Annual Report Analyses

The following reports are needed as requested for annual reporting purposes

5.15.1. *Clinical Investigator Brochure*

- Summary of SAE (patients on therapy).
- Summary of deaths reported (patients on therapy).
- Summary of Patient disposition.
- Summary of primary reason for treatment discontinuation.
- Listing and summary of treatment-emergent adverse events –by CTCAE category and term.

5.15.2. *Development Safety Update Report*

- Cumulative Subject Exposure by Age Group and Sex
- Cumulative Subject Exposure by Racial Group

- Estimated Cumulative Subject Exposure
- Subject Exposure by Gender
- Listing of Patients Who Discontinued Due to Adverse Event
- Listing of Deaths

5.16. Clinical Trial Registry Analyses

[figure not shown]
For the purpose of fulfilling the Clinical Trial Registry requirements, summaries of SAEs (whether treatment emergent or not) and 'Other' AEs (that is, non-serious TEAEs) by PT and treatment group will be performed. For each PT, the number of patients at risk, patients who experienced the event, and events will be presented. In addition, the summary will be provided as a dataset in XML format.

6. References

7. Appendices

Appendix 1. Flow Chart of PFS Censoring Rules

Abbreviation: PD = progressive disease
